3.5.1.5. Analyses for Medically Attended RSV LRTI beyond the Primary Endpoint

The following analyses will be conducted on the ITT population and based on observed events, unless stated otherwise.

The incidence of medically attended RSV LRTI that occurred > 150 days post dose and ≤ 360 days post dose will be summarized by treatment group. ITT subjects who remained in the study at the Day 151 visit will be used as the denominator to calculate the incidence rate for the summary of the incidence > 150 days post dose, and the ITT population will be used for the summary of the incidence ≤ 360 days post dose.

Age at onset of the first medically attended RSV LRTI will be tabulated by age group used for randomization stratification by treatment group. In addition, time-to-first medically attended RSV LRTI will be plotted at subject's level along the axis of age at birth.

The incidence of medically attended RSV LRTI by subtype (RSV A, RSV B) through 150 days post dose, > 150 Days and through 360 days post dose will be summarized by treatment group. The populations that the summary will be based on will be similar to what had been used for the analysis of medically attended RSV LRTI at each corresponding time period.

To capture and summarize multiple medically attended RSV LRTIs, the total number of new onset medically attended RSV LRTIs since the previous medically attended RSV LRTI will be calculated for each subject. A new onset medically attended RSV LRTI is defined as an adverse event (AE) meeting protocol specified medically attended RSV LRTI that occurred at least 14 days after the resolution date of the previous AE for a medically attended RSV LRTI. Similar definition is applied with a 30 days interval between the resolution of the previous event and a new onset of event (see [Table 3.5-1](#) for details). A listing will be generated to provide the following information: age at randomization, hemisphere, total number of events (at least 14 days apart), total number of events (at least 30 days apart), days to event, adverse event (AE) verbatim term, Date of AE onset/stop, Days from previous event, Visit setting, and RSV subtype. AEs associated with medically attended RSV LRTI will be summarized overall, as well as categorized by MedDRA system organ class (SOC) and preferred term (PT). Summaries will be presented through 150 days, after 150 days, and through 360 days.

3.5.1.6. Sensitivity Analyses for Subjects who are Not Followed through 150 Days Post Dose

Sensitivity analyses for RSV LRTI through 150 days post dose will be performed to address subjects who do not have an RSV LRTI and are not followed through 150 days post dose through various approaches of missing data imputation are described as follows:

1. Subjects who do not have an RSV LRTI and are not followed through 150 days post dose will be counted as having not met the RSV LRTI endpoint.
2. Impute the missing values in each treatment group using 2-times the placebo RSV LRTI event rate through 150 days post dose (ie, Bernoulli distribution with expected value equal to 2-times placebo RSV LRTI event rate).
3. Tipping point analysis by imputing the missing values in the MEDI8897 arm using 2-times the placebo event rate through 150 days post dose and imputing the missing

values in the placebo arm with the placebo rate (ie, Bernoulli distribution with expected value equal to 2 or 1-times placebo RSV LRTI event rate).

4. Tipping point analysis by imputing the missing values in the MEDI8897 arm using 3-times the placebo event rate through 150 days post dose and imputing the missing values in the placebo arm with the placebo rate (ie, Bernoulli distribution with expected value equal to 3 or 1-times placebo RSV LRTI event rate)
5. Subjects who do not have an RSV LRTI and are not followed through 150 days post dose will be counted as having met the RSV LRTI endpoint.
6. Multiple imputations
7. Impute the missing values in each treatment group using 1-time, 2-time, and 3-time the overall placebo event rate in single imputation approach.

The sensitivity analyses 2-4 will be conducted following the steps below:

- Step 1: Determine the observed placebo RSV LRTI rate through 150 days post dose, which is calculated as the proportion of all randomized placebo subjects with observed RSV.
- Step 2: Impute the event status for subjects who do not have an RSV LRTI and are not followed through 150 days post dose in each treatment arm or the MEDI8897 arm only (depending on the sensitivity analysis planned above) using the Bernoulli distribution with X-times the observed placebo RSV LRTI rate without involvement of stratification factors.
- Step 3: The subjects with imputed values of RSV LRTI status (Yes/No) will be combined with the remaining subjects who either have an RSV LRTI prior to 150 days post dose or who were followed through 150 days post dose without an RSV LRTI, to form a complete dataset.
- Step 4: Analyze the complete dataset using a Poisson regression model with robust variance to compare the incidence of medically attended RSV LRTI between MEDI8897 and placebo, including treatment group, and two stratification factors (age group and hemispheres) as covariates. The point estimate of log-transformed RR and its variance will be produced from the model.
- The steps 2-4 will be repeated 20 times with seed 1-20, respectively. SAS procedure PROC MIANALYZE will be used to combine inferences from the 20 completed datasets, which will result in a combined point estimate of log-transformed RR and the variance.

For sensitivity analyses 1 and 5, all subjects who do not have an RSV LRTI and are not followed through 150 days post dose will be assumed to either (1) have an RSV LRTI event

(sensitivity analysis #5) or (2) not have an RSV LRTI event (sensitivity analysis #1). The subjects with imputed values of RSV LRTI status will be combined with the remaining subjects who either have an RSV LRTI prior to 150 days post dose or who were followed through 150 days post dose without the event to form a complete dataset. The primary efficacy analysis model will be used to analyse the completed datasets via the specified imputation method.

For sensitivity analysis 6, the medically attended RSV LRTI event status for the subjects who do not have an RSV LRTI and are not followed through 150 days post dose will be imputed by the observed event rate per treatment group. That is, following the standard Multiple Imputation procedure and carried by Proc MI (Monotone Logistic Regression Method) and PROC MIANALYZE.

For sensitivity analysis 7, the number of medically attended RSV LRTI events for those MEDI8897-treated subjects who dropped out prior to Day 150 post dose without the event will be generated using a binomial distribution with 1-time, 2-time, or 3-time observed placebo event rates, respectively. While placebo-treated subjects who dropped out prior to Day 150 post dose without the event will be imputed using a 1-time observed placebo rate. With the imputed number of events, the RR reduction and the 95% CI will be constructed using an exact conditional method based on the number of RSV LRTIs (Breslow and Day, 1987). This analysis will be carried out by StatXact PROC Poisson procedure.

3.5.1.7. Subgroup Analyses for the Primary Efficacy Endpoint

Subgroup analysis will be performed for the primary efficacy endpoint, the incidence of medically attended RSV LRTI. Treatment-by-subgroup interaction will be tested using the Poisson regression with robust variance model with the terms of treatment, age group, hemisphere, subgroup, and treatment-by-subgroup interaction, which will be implemented using PROC GENMOD procedure. If this full model does not achieve convergence, a reduced model of treatment, subgroup, and treatment-by-subgroup interaction will be used. Significant treatment-by-subgroup interaction is judged at the significance level of 0.10. Within each level of a subgroup, the RR reduction and its corresponding 95% CI will be estimated using a Poisson regression model with robust variance with the term of treatment. A forest plot of the RR reduction and the 95% CI will be presented. In the event that the Poisson regression model does not converge for any stratum of a subgroup, the exact conditional method based on the number of RSV LRTIs (Breslow and Day, 1987) will be used as the analytical model to generate the relative risk reduction and its corresponding CI for all subgroup strata. This model will be implemented by StatXact PROC Poisson procedure and the point estimate and mid-p adjusted 95% CI will be reported.

The subgroup analysis will be conducted for the following subgroups on the ITT population:

- Hemisphere
- Age at randomization stratum (age \leq 3 months, age $>$ 3 to \leq 6 months, age $>$ 6 months)
- Gender
- Race (Caucasian, non-Caucasian)
- Weight at birth (weight \leq 2.5 kg, weight $>$ 2.5 kg)
- Weight on Day 1 (weight \leq 2.5 kg, weight $>$ 2.5 to \leq 5 kg, weight $>$ 5 kg)
- GA (29-32 weeks, $>$ 32 weeks)
- Sibling also participating in the study (yes/no)

In addition, incidence of medically attended RSV LRTI will be summarized by Country.

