had no effect on PK or the safety profile. These results demonstrated an acceptable safety profile for MEDI8897.

The Phase 1b/2a first-in-pediatric study (D5290C00002) is an ongoing, randomized, double-blind, placebo-controlled, dose-escalation study designed to evaluate the safety and tolerability, PK and ADA for MEDI8897 in healthy preterm infants of 32 - 35 wGA who would not receive RSV prophylaxis based on the AAP ([American Academy of Pediatrics Committee on Infectious Diseases, 2014](#)) or any other local or national recommending bodies' guidelines. This study population was selected based on advice from the United States Food and Drug Administration (US FDA) to perform initial clinical evaluations of MEDI8897 in a population where the benefit of RSV prophylaxis has been proven. Enrolment and dosing have been completed in 89 infants from sites in the United States, Chile, and South Africa. Infants were randomized and received a single IM dose of 10 mg, 25 mg, or 50 mg MEDI8897 (N = 71) or placebo (N = 18). All subjects are being followed for 1 year. The first interim analysis was conducted 30 days (October 2015) after the last subject was dosed to evaluate MEDI8897 serum concentrations, ADA, and safety. At the interim analysis, 1 infant in the placebo group had been withdrawn from the study because the mother could no longer bring the infant in for follow-up visits. At study entry, infants had a mean age (\pm SD) and mean weight (\pm SD) of 6.95 (\pm 2.63) months and 7.31 (\pm 1.84) kg in the placebo group and 6.50 (\pm 2.64) months and 6.82 (\pm 1.90) kg in the MEDI8897 group. MEDI8897 serum concentrations were consistent with the expected extended $t_{1/2}$ in infants. Model-based simulations predict the MEDI8897 median $t_{1/2}$ to range from 83 to 94 days for the 50 mg dose in infants with normal clearance. In healthy preterm infants the safety profile of MEDI8897 was favorable with similar proportions of AEs reported in the placebo (12/18, 66.7%) and MEDI8897 (51/71, 71.8%) recipients. No safety signals were observed with the ascending dose levels. There was 1 serious adverse event (SAE) that occurred in an infant who received 25 mg of MEDI8897. The infant was hospitalized for LRTI and, upon subsequent testing, was found to be negative for RSV by the real time reverse transcriptase-polymerase chain reaction (RT-PCR) assay. The illness resolved. All of the AEs were Grade 1 or 2 in severity. The most frequently reported AEs were URTI (placebo, 7/18, 38.9%; MEDI8897 27/71, 38%), anemia (placebo 5/18, 27.8%; MEDI8897, 9/71, 12.7%), cough (placebo 2/18, 11.1%; MEDI8897, 9/71, 12.7%), pyrexia (placebo 0, MEDI8897, 8/71, 11.3%), bronchiolitis (placebo 5.6%, MEDI8897 7/71, 9.9%), and rhinorrhea (placebo, 1/18, 5.6%; MEDI8897 7/71, 9.9%). There were no AESIs, NOCDs, or deaths. ADA levels at the 30-day interim analysis were similar for placebo and MEDI8897 recipients, with rates of 12.5% (2/18) and 4.4% (3/71) for placebo and MEDI8897 recipients, respectively. A second interim analysis is planned for 6 months after the last subject was dosed (March 2016) to evaluate MEDI8897 serum concentrations, ADA, and safety.

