2.1.2 Secondary Study Objectives

1. To assess the efficacy of MEDI8897 for the reduction of hospitalizations due to RT-PCR-confirmed RSV, compared with placebo
2. To evaluate the safety and tolerability of MEDI8897 when administered as a single fixed IM dose, compared with placebo
3. To evaluate single-dose serum concentrations of MEDI8897

4. To evaluate ADA responses to MEDI8897 in serum

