2.3 Treatment Assignment and Blinding

An interactive web response system (IWRS) will be used for randomization to a treatment group and assignment of blinded investigational product kit numbers. A subject is considered randomized into the study when the investigator notifies the IWRS that the subject meets eligibility criteria and the IWRS provides the assignment of blinded investigational product kit numbers to the subject.

Subjects will be randomized at a 2:1 ratio to receive a 50 mg IM dose of MEDI8897 (N = 1,000) or placebo (N = 500). Randomization will be stratified by temperate zones in the northern and southern hemisphere and by subject age group at randomization (ie, ≤ 3 months, > 3 to ≤ 6 months, > 6 months). Enrollment of infants > 6 months of age will be limited to approximately 500.

The procedure for using IWRS is as follows:

- The investigator or designee contacts the IWRS and provides the subject identification (SID) number and subject's baseline characteristic(s) used to verify that it is the same subject
- Placebo (provided by site) or a vial from a MEDI8897 kit will be assigned to the subject

- Confirmation of this information is sent to the unblinded investigational product manager who prepares the investigational product to be dispensed to the subject per the response system and records the appropriate information in the investigational product accountability log

Investigational product (MEDI8897 or placebo) must be administered the same day the investigational product is assigned. Total in-use storage time from needle puncture of the investigational product vial to administration should not exceed 4 hours at room temperature. If storage time exceeds these limits, a new vial should be used. If there is a delay in the administration of investigational product such that it will not be administered within the specified time frame, the unblinded investigational product monitor must be notified immediately.

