2.4 Sample Size

The sample size of 1,500 subjects is necessary based on advice from the United States Food and Drug Administration US FDA requesting that 1,000 preterm infants be exposed to MEDI8897 in this Phase 2b study. This sample size has approximately > 99% power to detect 70% relative-risk reduction, assuming a placebo group medically attended RSV LRTI incidence of 8%. Power calculations are based on a Poisson regression model with robust variance (Zou, 2004) comparing MEDI8897 50 mg versus placebo, with 2-sided, $\alpha = 0.05$.

- The 70% relative-risk reduction assumption is based on a placebo-controlled study in Native American infants in which there was 87% relative reduction in the incidence of RSV hospitalization (11.3% placebo; 1.5% motavizumab; $p < 0.001$) and 71% relative reduction in the incidence of outpatient RSV LRTI (10.0% placebo; 2.9% motavizumab; $p < 0.001$) in infants who received motavizumab prophylaxis (O'Brien et al, 2015)

In order to evaluate risk, a sample size of 1,000 subjects exposed to MEDI8897 will provide a 90% probability of observing at least one AE if the true event rate is 0.2%; if no AEs are observed, this study provides 95% confidence that the true event rate is < 0.3%.

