3 STATISTICAL METHODS

3.1 General Considerations

Summary statistics will be tabulated by treatment group. Categorical data will be summarized by the number and percentage of subjects in each category. Continuous variables will be summarized by mean, median, standard deviation, minimum, and maximum. In general, unless stated otherwise, baseline will be defined as the last non-missing value prior to dosing.

There are two planned analyses for this study: the Primary Analysis and the Final Analysis. The Primary Analysis will be conducted after all randomized subjects have completed the Day 151 visit. At the time of this primary analysis, approximately half of all subjects enrolled (722 subjects) will have completed the Day 361 visit. The remaining 731 subjects will have completed approximately 8 months of the study. MEDI8897’s efficacy will be evaluated in the Primary Analysis as intended by the study design. In addition, all available PK, ADA, and safety data will be analyzed. The final analysis will be conducted when all subjects have completed the last visit of the study.

Data analyses will be conducted using the SAS® System Version 9.3 or higher (SAS Institute Inc., Cary, NC) in a SAS GRID environment.

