3.4.3 Study Drug Exposure

Due to the simplicity of dosing for this study, exposure is summarized in the Subject Disposition and Completion Status table under “Randomized and dosed.” No other summary will be reported.

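### Under a fixed 50 mg dose, the three-bin test of effect by Day 1 weight is often not estimable and has low power for a gradual decline; pre-specify a continuous-weight interaction beside it

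*SAP*

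**What the plan says.** SAP v5 section 2.3 has infants "randomized at a 2:1 ratio to receive a 50 mg IM dose of MEDI8897", and section 2.1.2 describes administration "when administered as a single fixed IM dose, compared with placebo". The dose is therefore not scaled to weight.

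Section 3.5.1.7 lists the subgroup as "Weight on Day 1 (weight \leq 2.5 kg, weight $>$ 2.5 to \leq 5 kg, weight $>$ 5 kg" and fits a modified Poisson model with treatment, age group, hemisphere, subgroup and treatment-by-subgroup terms. On the interaction: "Significant treatment-by-subgroup interaction is judged at the significance level of 0.10". There are two fallbacks. If the full model fails to converge, age group and hemisphere are dropped and the interaction is kept. If the model fails within a level of a subgroup, an exact conditional method supplies the estimates and mid-p intervals for all levels. No continuous-weight term and no power for any interaction test appear in the plan.

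Related material lies elsewhere. Section 3.4.2 tabulates Day 1 weight overall and by age category, country and hemisphere. Section 3.9 summarises serum concentrations and PK parameters, illustrates them by ADA status and LRTI outcome, and leaves the detail to a separate PK report. Protocol section 3.2.3 plans an exposure-response analysis of serum concentration against the efficacy endpoints.

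**The concern.** At 50 mg, the dose is 50/2.5 = 20 mg/kg at 2.5 kg, 50/5 = 10 mg/kg at 5 kg and 50/10 = 5 mg/kg at 10 kg. Protocol section 1.4 predicts the median half-life "to range from 83 to 94 days for the 50 mg dose in infants with normal clearance". Suppose concentration scaled as 1/weight with a common half-life and no growth, all of which are simplifications. A 10 kg infant would then reach any given concentration one half-life, 83-94 days, before a 5 kg infant. A decline in effect with weight is thus a natural question for a trial of one fixed dose over 150 days.

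The test that is meant to answer it spends two degrees of freedom on three bins, ignores the ordering of weight, and relies on six arm-by-bin cells that share few events. If it comes back non-significant, a reader may take that as support for equal protection at all weights, which it could not provide.

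**Working it through.** **1. The plan's own figure.** SAP v5 section 2.4: "The sample size of 1,500 subjects is necessary", 2:1, placebo incidence 8%, relative risk reduction (RRR) 70%, two-sided 0.05, power above 99%.

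- Active incidence: 0.08 × 0.30 = 0.024.
- Expected events: 500 × 0.08 = 40 and 1,000 × 0.024 = 24, so 64.
- Variance of log RR: 0.92/40 + 0.976/24 = 0.0230 + 0.0407 = 0.0637; SE = 0.252.
- z = 1.204/0.252 = 4.77; power = Φ(4.77 − 1.96) = 99.8%.

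A two-proportion calculation gives 99.6%. The stated figure is reproduced. Section 3.1 counts 722 subjects past Day 361 and adds "The remaining 731 subjects will have completed approximately 8 months of the study", so 722 + 731 = 1,453 (969/484 at 2:1). Expected events are then 38.7 + 23.3 = 62, and power is 99.7%.

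**2. Why a cell is often empty.** Assume a share s of infants at or below 2.5 kg and RRR 82% there, so active risk is 0.08 × 0.18 = 0.0144.

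- s = 5%: P(no active event) = 0.9856^48.5 = 0.50; P(no placebo event) = 0.92^24.2 = 0.13; at least one empty cell: 1 − 0.50 × 0.87 = 0.56.
- s = 10%: 0.9856^96.9 = 0.25 and 0.92^48.4 = 0.02; at least one empty cell: 1 − 0.75 × 0.98 = 0.26.

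With an empty cell, the log relative risk in that bin runs off to infinity and the 2-df Wald test is not usable. Dropping age and hemisphere leaves the cell empty. The exact conditional method returns estimates by bin, not an interaction test.

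**3. Simulated power of the interaction test at 0.10.** N = 1,453, placebo 8%, modified Poisson with robust variance, age group and hemisphere in the model. Assumed weights: age-stratum means 3.6, 5.9 and 7.6 kg, within-stratum SDs about 1 kg, and 15% or 32% of infants over 6 months. Moderate decline: RRR 82% at 3 kg, 70% at 5, 55% at 7.5 and 40% at 10. Steep decline: 86% down to 15%.

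| Scenario | Three bins, when estimable | Two bins (cut at 5 kg) | Continuous log-weight |
|---|---|---|---|
| Moderate decline | 14-15% | 29-30% | 36% |
| Steep decline | 31-36% | 54-56% | 63-66% |

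An arm-by-bin cell was empty in 39-64% of trials with a declining effect. For the moderate decline, the three-bin test has 15/36, about 0.4, of the continuous term's power; for the steep one, about half. Separate runs of the same design gave:

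- Step at 5 kg (RRR 82% below, 55% above): two bins 51-52%, continuous term 42-44%.
- No interaction: three bins reject in 5% of trials, continuous term in 11%.

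**4. A different weight model.** Normal weights, SD 1.9 kg, truncated to 1.6-11 kg, mean 4.5, 5.5 or 6.8 kg; N = 1,500; overall RRR held at 70%; no covariates.

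- Relative risk rising smoothly 2- to 5-fold from 3 to 9 kg: three bins 5-41%, continuous term 20-61%.
- Three-fold step at 5 kg in the lightest mix: three bins 53-60%, continuous term 53-55%.
- Empty cells: 13-41%, 53-80% and 93-98% of trials as mean weight rises.

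**The case against.** The strongest reply is that other parts of the plan already address the question. Measured concentration lies closer to the mechanism than Day 1 weight does, and protocol section 3.2.3 plans to relate it to efficacy. Age at randomization, with a level above 6 months, is a further interaction subgroup. These subgroup tests carry no confirmatory claim. The binding limit is about 64 events, not the form of the test: the continuous term also misses the moderate decline in most trials (36% power). Every weight mix and effect curve above is assumed.

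Most of this stands, and it limits the point to an inexpensive improvement. It does not remove it: none of the alternatives is a pre-specified test of efficacy by weight, and SAP v5 section 3.9 names plots by ADA status and outcome, not by weight.

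Two stronger readings are tempting.

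- **The open-ended top bin is the cause.** Two bins with the same open top recover much of the loss (29-30% against 14-15%; 54-56% against 31-36%). Most of the deficit therefore comes from the sparse lowest bin and the extra degree of freedom, and splitting the top bin would not help the test.
- **Exposure goes otherwise unreported.** Section 3.4.3 does say "No other summary will be reported", but it concerns the count of infants dosed. Serum exposure is covered in section 3.9 and weight in section 3.4.2; with one fixed dose, mg/kg is simply 50/weight.

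**Conclusion.** The point holds in a limited form. The planned weight interaction will often not be properly estimable (an empty cell in 39-64% of simulated trials with a declining effect). When it is, its power for a gradual decline is roughly half or less that of a 1-df continuous term: 14-15% against 36% for a moderate decline, 31-36% against 63-66% for a steep one.

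These figures rest on an 8% placebo rate, 1,453 infants, assumed weight distributions and assumed effect curves. The direction was the same under a quite different weight model for smooth declines. It does not hold for every shape: for a sharp step at 5 kg a two-bin test does better than the continuous term, and in a light population the existing three bins match it.

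A reader might infer that a continuous term would settle whether protection holds in heavier infants. The figures do not support that: it is better, but still underpowered for moderate declines. Nor do the documents show that protection does decline with weight, and nothing here bears on the choice of dose. The effect on the trial's conclusions is confined to how a non-significant weight interaction is read.

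**What to change.** In SAP section 3.5.1.7:

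- Pre-specify a 1-df treatment by log(Day 1 weight) interaction at 0.10, with treatment, log-weight, age group and hemisphere in the model.
- Plot the model-based RRR with its 95% CI across the observed weight range.
- Keep the three weight bins as descriptive forest-plot rows.
- State that a non-significant interaction is not evidence of equal protection across weights.
- State that the result will be read with the exposure-response analysis in protocol section 3.2.3, and that this model cannot separate weight from age, because the two move together and it has no treatment-by-age term.

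The cost is a few lines of SAP text, one model and one plot, on data already collected. The downside is that the term assumes a monotone effect of weight and is weaker than a two-bin test for a sharp step at 5 kg; the retained bins let a reader look for departures from that shape.

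### The subgroup fallback to the exact method depends on non-convergence, not on zero events in an arm, so a sparse level can keep a meaningless interval, and the interaction test has no rule for an empty cell

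*SAP*

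**What the plan says.** The governing text is SAP version 5, Section 3.5.1.7.

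- Estimation: "Within each level of a subgroup, the RR reduction and its corresponding 95% CI will be estimated using a Poisson regression model with robust variance"; treatment is the only term.
- Fallback for the estimate: "In the event that the Poisson regression model does not converge for any stratum of a subgroup", all levels of that subgroup move from the Poisson model to the exact conditional method. Its output is also stated: "the point estimate and mid-p adjusted 95% CI will be reported".
- Interaction: a robust-variance Poisson model with treatment, age group, hemisphere, subgroup and their treatment interaction. The only rescue is this: "If this full model does not achieve convergence, a reduced model of treatment, subgroup, and treatment-by-subgroup interaction will be used". The threshold for calling an interaction significant is a p-value of 0.10.

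The section sets no rule based on the number of events and no minimum level size. It does not state the convergence criterion, nor whether the interaction is tested by a Wald, score or likelihood-ratio statistic. By contrast, the fallback for the primary model in Section 3.5.1.2 can be triggered by a stratum that is too small as well as by non-convergence. The SAP versions before version 4 limited subgroup analyses to levels with sizable numbers; version 5 carries no such condition.

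**The concern.** The data feature that breaks the Poisson fit is an arm with no events. Non-convergence is only one possible symptom of it, and whether software reports that symptom depends on its stopping rule. If the symptom is missed, the forest plot shows perfect efficacy with a zero-width interval in a level that holds almost no information.

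The interaction test is exposed separately. The exact method is specified for the RRR and its interval only. The reduced interaction model drops age group and hemisphere but keeps the treatment-by-subgroup cells, so an empty cell remains empty. A false signal here would bear on how consistent the effect looks across subgroups.

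**Working it through.** **Inputs.** SAP Section 2.4: placebo incidence 8%, RRR 70%, so MEDI8897 incidence = 0.08 × 0.30 = 2.4%; 1,000 against 500 infants; two-sided alpha 0.05. Section 3.5.1.7: interaction level 0.10. Subgroup level sizes are not in the documents, so those below are assumptions.

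**1. The plan's own figure.** "This sample size has approximately > 99% power to detect 70% relative-risk reduction". Robust Poisson SE of log RR = √[(1 − 0.024)/24 + (1 − 0.08)/40] = √0.0637 = 0.252. |log 0.3|/0.252 = 1.204/0.252 = 4.77, and Φ(4.77 − 1.96) = 99.75%. The stated power is reproduced.

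**2. Why the robust SE stays finite.** In an arm of n infants with no events and fitted mean μ, the sandwich variance of the log rate is nμ²/(nμ)² = 1/n. It does not grow as μ tends to zero. The SE of log RR is therefore √[1/n₁ + (1 − p₀)/x₀], with n₁ the size of the empty arm and p₀, x₀ the event proportion and count in the other arm.

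**3. Zero-event examples** (MEDI8897 against placebo; statsmodels Poisson GLM, HC0 variance).

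| Table | Fit status | Robust SE | RRR (95% CI), Poisson | RRR (95% CI), mid-p |
|---|---|---|---|---|
| 0/60 vs 2/30 | converged, 20 iterations | √(1/60 + 0.9333/2) = 0.695 | 100% (100%, 100%) | 100% (−74%, 100%) |
| 0/100 vs 4/50 | converged | √(1/100 + 0.92/4) = 0.490 | 100% (100%, 100%) | 100% (44%, 100%) |

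In the first table the fitted log RR is −21.8 and p is about 1e-215. The mid-p limit follows by hand. With 2:1 sizes, an event falls on placebo with probability q = 1/(1 + 2RR). Setting 0.5q² = 0.025 gives q = 0.2236 and RR = 1.74, so the RRR limit is −74%. Without the mid-p adjustment, q² = 0.025 gives RR = 2.66 and −166%.

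**4. Dependence on the stopping rule.** In 0/60 vs 2/30 each Newton step moves the log RR by about −1. A deviance rule (1e-8) is met. A relative-parameter rule (1e-4) is not met within 50 iterations; the relative change there is still about 0.02. The same data thus trigger the fallback under one rule and not under the other.

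**5. Interaction.** Add a second level with 24/909 vs 37/454, where log RR = −1.13.

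- Wald: coefficient −20.0; SE = √[0.4833 + 0.9736/24 + 0.9185/37] = √0.5487 = 0.741; p about 1e-160.
- Generalized (robust) score: p = 0.146.
- Likelihood ratio: p = 0.16.

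Only the Wald test rejects at 0.10.

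**6. How often.** P(no MEDI8897 events) = 0.976ⁿ, with n the MEDI8897 infants in the level: 50, 30%; 75, 16%; 100, 9%; 333, 0.03%. The last is about the MEDI8897 share of the oldest age stratum at its cap of roughly 500.

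In 20,000 simulated trials per size, with a common RR of 0.3 and draws with no event in either arm of the level excluded, the Wald interaction test at 0.10 rejected as follows:

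| Level size (both arms, 2:1) | Rejection rate |
|---|---|
| 60 | 47% |
| 90 | 30% |
| 150 | 14% |
| 300 | 9% |

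The generalized score test, run on up to 1,500 of these trials per size, rejected in 4% to 14%.

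**The case against.** The strongest reply is that with zero events the maximum likelihood estimate is minus infinity, so mathematically the model does not converge and the exact fallback already applies. SAS PROC GENMOD, which the SAP names, might also flag the fit. Either would remove the bad interval. This stands as a limit on the claim: SAS was not run. It does not settle the matter, because the SAP does not define non-convergence and a programmer will normally act on what the software reports.

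A reader might infer that the interaction test will be declared significant whenever a cell is empty. The documents do not support that. They do not name the statistic, and on the same data the score and likelihood-ratio tests are not significant. The p-value near 1e-160 belongs to a Wald test only.

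It is also fair that version 5 already limits sparse modelling. Country, RSV subtype and the hospitalization subgroups are summarized without a subgroup model, and a printed interval of 100% to 100% would probably catch a reviewer's eye. A Wald interaction p-value is less obviously wrong on the page.

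**Conclusion.** The point holds as a defect in the fallback rule, of moderate importance. As written, whether a zero-event level gets a usable interval depends on an unstated software criterion; where the fit is accepted, the error bar is wrong by a wide margin (a lower limit of 100% where mid-p gives −74%). The interaction test lacks any rule for an empty cell, and whether it misleads depends on an unnamed statistic.

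This rests on assumed level sizes, the SAP's planning incidences, and fits in statsmodels rather than SAS. The risk is material for levels of about 150 infants or fewer and negligible for large ones. Section 3.5.1.7 does not say whether dropouts are imputed within subgroups; the calculations use observed counts.

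A reader might take this as a threat to the trial's efficacy conclusion. It is not: the primary test, the hierarchical test of RSV hospitalization and the type I error are untouched. What is affected is the forest plot and the reading of consistency across subgroups.

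**What to change.** In SAP Section 3.5.1.7:

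1. Use the exact conditional mid-p method for all levels of a subgroup if either arm in any level has zero events, or if the Poisson model does not converge.
2. Specify the generalized score test for the treatment-by-subgroup interaction, and report no Wald interaction p-value when any treatment-by-subgroup cell has zero events.

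The first change alone would not repair the interaction test, because the exact method is never used there. The cost is a few sentences, some extra specification and programming for the score test, and wider intervals in sparse subgroups. The exact procedure for the estimates is already planned. Both rules can be fixed before unblinding.
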